PARTNERS HUMAN RESEARCH COMMITTEE PROTOCOL SUMMARY

Answer all questions accurately and completely in order to provide the PHRC with the relevant information to assess the risk-benefit ratio for the study. Do not leave sections blank.

PRINCIPAL/OVERALL INVESTIGATOR

[name]

PROTOCOL TITLE

An online pilot study of Version 2 of the smoking cessation smartphone app "Smiling instead of Smoking" (SiS)

FUNDING

American Cancer Society

VERSION DATE

October 25, 2018

SPECIFIC AIMS

Concisely state the objectives of the study and the hypothesis being tested.

The overall goal of this pilot study is to solicit feedback from nondaily smokers looking for smoking cessation support online (n=270) about Version 2 of a smartphone app we designed to support smoking cessation. Feedback will be collected via passively collected smartphone app usage data, surveys and, in a sub-sample (n=20), online video-conference user feedback sessions. Results will be used to guide the design of Version 3.0 of the "Smiling Instead of Smoking" (SiS) smartphone app. Specifically, our aims are to:

- (1)Assess ease-of-use and helpfulness of the app, as rated by app users 6 weeks after their chosen smoking cessation date
- Test if within-person changes occur in theorized mechanisms of (2) behavior change as nondaily smokers undergo a SiS app assisted quit attempt
- Identify app features in need of improvement, as identified by (3) passively recorded app usage patterns, REDCap open-ended survey items, and, in a sub-sample, user feedback sessions (n=20)

BACKGROUND AND SIGNIFICANCE

Provide a brief paragraph summarizing prior experience important for understanding the proposed study and procedures.

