To address this need, we are in the process of developing a smartphone app that acts as a behavioral, in-the-pocket coach and uses positive psychology exercises to enhance guitting success. Treatment via smartphone app is promising given the demonstrated effectiveness of texting interventions. It is particularly appealing because it is anonymous, portable, and provides just-in-time support, an important feature for smokers who smoke under specific conditions and circumstances. To support treatment, we use a positive psychology approach. Positive affect enhancement is an empirically sound treatment target: positive affect is psychometrically and neurologically distinct from negative affect, and plays an important role in the days leading up to and following a guit attempt. Enhancing positive affect with brief, self-administered exercises is entirely feasible: in recent years, a large number of positive psychology exercises have been developed that have consistently led to improvements in happiness, reductions in depression, and improvements in overall well-being. The smartphone app administers such positive psychology exercises to enhance and/or maintain positive affect, which is hypothesized to stimulate nondaily smokers to enact healthier alternatives to smoking by broadening their thought-action repertoire, increasing confidence, and decreasing craving and defensiveness about smoking-related health information (Figure 1). The focus on happiness will help overcome treatment resistance, as the pursuit of happiness is generally appealing and non-stigmatizing. To this end, we have worked closely with nondaily smokers in Study 1 (#2017P001106) to develop Version 2 of our "Smiling Instead of Smoking" app. In the current study (i.e., Study 2 in a series of 3 studies funded by the American Cancer Society (130323-RSG-17-021-01-CPPB)), we will conduct a larger pilot study to gain feedback from nondaily smokers on Version 2. Study 3 will be a proof-of-concept RCT of Version 3 of this app.

[figure not shown]

Figure 1. Treatment mechanism.

RESEARCH DESIGN AND METHODS

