Briefly describe study design and anticipated enrollment, i.e., number of subjects to be enrolled by researchers study-wide and by Partners researchers. Provide a brief summary of the eligibility criteria (for example, age range, gender, medical condition). Include any local site restrictions, for example, "Enrollment at Partners will be limited to adults although the sponsor's protocol is open to both children and adults."

An estimated 270 participants will participate (i.e., sign consent) in this study based on the following eligibility criteria: (a) 18+ years of age, (b) smartphone ownership (c) current nondaily smoker, who smokes at least weekly, and no more than 25 out of the past 30 days (i.e., 71% of nondaily smokers), (d) has current quit intention (i.e., 65-74% of nondaily smokers), and (e) interested in helping us develop a smartphone app for smoking cessation. We will stop enrollment when n=90 participants have completed the primary endpoint of the study, which is the 6-week follow-up. Our study will be conducted entirely remotely and will require a screening process prior to enrolling participants on the app. Based on our experience in Study 1 (#2017P001106), we expect that 1/3 of participants who initially provide consent will pass the screening process and be retained for the 6-week follow-up. Thus, we are estimating that n=270 will be necessary to sign the initial consent for this study in order for n=90 to complete the primary endpoint of this study.

Briefly describe study procedures. Include any local site restrictions, for example, "Subjects enrolled at Partners will not participate in the pharmacokinetic portion of the study." Describe study endpoints.

Participation will last 6 months, where surveys will be administered prior to the quit day (online, as part of a screening test), and at 2-week, 6-week, 3-month, and 6-month follow-ups of the participant's chosen quit day (Figure 2). Participants will use the

[figure not shown]

Figure 2. Timeline of Your Study Participation

app for a strongly encouraged period of 7 weeks (1 week before, 6 weeks following the quit attempt), and optional continued use thereafter.

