Participants will complete two types of assessment: (1) surveys, and (2) (in a sub-sample) user feedback sessions conducted via Skype. Potential participants will click-through to the study website. This website will explain that participants must call study staff in order to be phone-screened and to participate in the study. During the phone-screen, participants will be directed to complete an online survey via REDCap. Within the survey, participants will be asked if they would be willing to participate in an online video-conference user feedback session after they have used the app for seven weeks (1 week pre, 6 weeks post their chosen smoking quit day). Participation in the user feedback session is optional. Participants will receive survey links for 2-week, 6-week, 3-month and 6-month follow-ups via an emailed link. If selected for the online user feedback sessions (selected at random from interested participants), participants will receive an email and/or phone call upon completing their 6-week survey to set up the user feedback session.

The online user feedback sessions (n=20) will consist of the participants, and 1-2 members of the study staff. Relatively little guidance will be provided in this setting. Instead, 4 open-ended questions will be posed (i.e., did the app help you in your quit attempt? What did you like? What did you dislike? How could the app be improved?). All conference calls will be video-recorded for later analysis.

Sample size and Power Considerations: The primary goal of this study is to gather qualitative input rather than data to detect a pre-specified effect. The goal of this pilot study is to get input from app users who are interacting with the app and study staff completely remotely, without the benefit of inperson interaction, which is closer to the real-world experience potential users would have than the participants in Study 1. Thus, to identify issues not identified within the smaller sample in Study 1, we tripled the sample size of the current study, Study 2.

Planned Analyses:

Partners Human Subjects Research Application Form Version Date: October 15, 2014

Aim 1 (Ease-of-use and usefulness). To assess the degree to which SiS Version 2 is easy to use and perceived as useful by nondaily smokers attempting to quit smoking, we will use the Week 6 survey data, and will calculate means and standard deviations for the survey items querying ease of use and usefulness for each feature of the app.

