Aim 2 (Within-person changes). To test if nondaily smokers utilizing SiS Version 2 experienced changes over time on constructs theorized to underlie smoking cessation, we will use the online survey data and fit one repeated measures mixed effects model per construct of interest (i.e., desire to smoke, mood, self-efficacy to quit/stay quit, motivation), where the construct will be the dependent variable, and time (0=baseline, 1=2-week, 2=6-week, 3=3-month, 4=6-month) will be the predictor. Correlations over time will be modeled with an unstructured covariance matrix. A contrast statement will be used to compare baseline versus follow-up. Given the explorative nature of this study, we will not correct for multiple testing.

Aim 3 (Identify app features in need of improvement). To identify features of the app that are in need of improvement, we will examine the passively generated app usage data as nondaily smokers enrolled in our study undergo their quit attempts, and will generate descriptive summary statistics on these usage data. To gain deeper insight, we will also conduct user feedback sessions with a randomly selected subsample of participants.

For studies involving treatment or diagnosis, provide information about standard of care at Partners (e.g., BWH, MGH) and indicate how the study procedures differ from standard care. Provide information on available alternative treatments, procedures, or methods of diagnosis.

Not applicable.

Describe how risks to subjects are minimized, for example, by using procedures which are consistent with sound research design and which do not unnecessarily expose subjects to risk or by using procedures already being performed on the subject for diagnostic or treatment purposes.

Risks are expected to be minimal, and include breach of confidentiality, subject discomfort form answering questions about smoking, and discomfort from quitting smoking (see below). We will minimize these risks by safeguarding electronic data capture by using HIPAA-compliant electronic data capture processes, assuring participants that they do not need to answer any questions they do not want to answer, and by providing information on how to manage smoking cessation.

Describe explicitly the methods for ensuring the safety of subjects. Provide objective criteria for removing a subject from the study, for example, objective criteria for worsening disease/lack of

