improvement and/or unacceptable adverse events. The inclusion of objective drop criteria is especially important in studies designed with placebo control groups.

A subject will be removed from the study if he or she no longer wishes to participate for any reason. A subject may also be removed from the study by the PI, if he or she cannot comply with study procedures (e.g., responds incorrectly to survey check items, cannot install the app on his/her smartphone) or causes undue distress to study staff (e.g., becomes belligerent towards study staff).

FORESEEABLE RISKS AND DISCOMFORTS

Provide a brief description of any foreseeable risks and discomforts to subjects. Include those related to drugs/devices/procedures being studied and/or administered/performed solely for research purposes. In addition, include psychosocial risks, and risks related to privacy and confidentiality. When applicable, describe risks to a developing fetus or nursing infant.

Potential Risks: Participation will last 6 months, where surveys will be administered at enrollment, 2-week, 6-week, 3-month, and 6-month follow-up. Participants will use the app for a strongly encouraged period of 7 weeks (1 week before, 6 weeks following the quit attempt), and optional continued use thereafter. Additional tasks are potential participation in online video-conference user feedback sessions, as summarized in Figure 2. As such, the potential risks in the study are considered minimal and include (1) potential discomfort related to completing questionnaires about potentially sensitive information such as smoking, (2) potential breach of confidentiality and/or privacy, and (3) potential discomfort in quitting smoking (i.e., withdrawal symptoms, craving, etc.).

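### Does the pilot miss a result it needs because no planned output counts install failures and removals by reason?

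*Combined protocol and SAP*

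**What the plan says.** The objective removal criteria, in Research Design and Methods, allow but do not require the principal investigator to remove a subject "if he or she cannot comply with study procedures (e.g., responds incorrectly to survey check items, cannot install the app on his/her smartphone".

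The planned outputs are these:

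- **Aim 1.** Ease of use and helpfulness are to be assessed "as rated by app users 6 weeks after their chosen smoking cessation date" (Specific Aims). For this the team "will calculate means and standard deviations for the survey items querying ease of use and usefulness for each feature of the app" (Planned Analyses), using the Week 6 survey.
- **Aim 2.** One repeated-measures mixed model is fitted per survey construct, from baseline to 6 months.
- **Aim 3.** The sources are "passively recorded app usage patterns, REDCap open-ended survey items, and, in a sub-sample, user feedback sessions (n=20" (Specific Aims). For the app data, the team "will generate descriptive summary statistics on these usage data" (Planned Analyses). The content of those statistics is not itemised.

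For enrolment, Research Design and Methods gives one combined figure: "we expect that 1/3 of participants who initially provide consent will pass the screening process and be retained for the 6-week follow-up". From this come 270 consents for 90 Week 6 completers, and enrolment stops once 90 have completed. Sample size and Power Considerations says the sample was tripled "to identify issues not identified within the smaller sample in Study 1". Background and Significance adds that "Study 3 will be a proof-of-concept RCT of Version 3 of this app".

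**The concern.** The team foresaw that some people would be unable to install the app, since it names this as a ground for removal. Eligibility asks only for smartphone ownership, so an owner whose phone cannot run the app is not clearly excluded beforehand. Once removed, that person gives no Week 6 rating, generates no usage data and cannot reach a feedback session, because those are arranged after the Week 6 survey. Installing an app without in-person help is also just the sort of difficulty a remote pilot might be expected to reveal.

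The single 1/3 adds to the impression, because it merges failing the screen with being lost afterwards. If no planned result separated the two, the team might go into Version 3 and the randomised Study 3 without knowing which step loses people. Counts could be rebuilt later from consent and app records, but the reason for an install failure could not, unless someone recorded it when it happened.

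**Working it through.** **1. Reproduce the plan's figure.** Inputs from Research Design and Methods: 90 completers, combined fraction 1/3. Consents needed = 90 / (1/3) = 270, as stated. Not reaching Week 6: 270 − 90 = 180, or 67%. No power calculation applies; the sample-size text says the main purpose is qualitative input.

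**2. See what the combined fraction leaves open.** 1/3 = screening-pass rate × Week 6 retention. The documents give only the product, so the pass rates below are assumptions.

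| Assumed pass rate | Screened in (270 × rate) | Without Week 6 survey (screened in − 90) | Share lost | Retention (90 / screened in) |
|---|---|---|---|---|
| 40% | 108 | 18 | 18/108 = 16.7% | 83.3% |
| 50% | 135 | 45 | 45/135 = 33.3% | 66.7% |
| 60% | 162 | 72 | 72/162 = 44.4% | 55.6% |

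Each row returns 90/270. The table shows that one product cannot be split into two factors. It says nothing about how many losses are install failures: the documents give no such rate, and none can be derived from 270, 90 and 1/3.

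**3. Ask whether non-installers belong in that table.** Research Design and Methods places a screening process before participants are enrolled on the app. The removal clause puts inability to install beside failed check items, and the remuneration text under Recruitment Procedures makes correct check items a screening criterion. The documents do not say whether installation is tried before or after screening closes. If before, install failures are screen failures and the 18, 45 or 72 contain none of them. If after, they are some unknown part.

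**4. Compare each aim with what it needs.**

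- Aim 1 is defined on app users. Someone who never had the app has no feature to rate, so leaving that person out matches the stated target. Because enrolment continues to 90 completers, install failures cost extra consents, not Week 6 respondents.
- Aim 2 uses survey data at five time points. Its analysis set is not defined. If it is the enrolled participants, comparing the number at baseline with the number at Week 6 gives the very split between screening and later loss that seemed unavailable.
- Aim 3 covers the usage data of enrolled participants. A count of those with no app data could fall within its descriptive statistics. It would not supply the reason.

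**5. Check whether the information would be lost.** Removal is the principal investigator's own decision on a stated ground, so the reason is known when it is made. Under Data and Safety Monitoring, the investigators review recruitment and retention every week. Under Monitoring and Quality Assurance, the principal investigator reviews the completeness of questionnaires, consent forms and app data in weekly meetings. The 1/3 itself comes from Study 1 experience, so the team already uses consent-to-completion figures for planning.

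**The case for a change.** The strongest reply is that weekly review is internal monitoring, not a result, and that it names neither installs nor reasons for removal. A study enlarged to find problems Study 1 missed should report the first remote step at which people can fail, and a reason not written down at the time is gone. One staff-entered field and one table would settle it, at almost no cost.

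Much of this is true. No section lists a participant-flow table or says that install failures are logged with a reason. A removed non-installer is indeed invisible to the Aim 1 ratings, the usage data and the feedback sessions. The documents also do not say whether follow-up surveys with failed check items are analysed, though that is a separate matter.

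What does not follow is that the plan is defective. Being able to install the app is not one of the three aims, so calling its count a missing result in effect adds an aim. The document is an ethics-committee summary whose form asks for a brief description; that it does not list a disposition table is weak evidence that none would be reported. That staff would leave the reason for a removal unrecorded is conjecture.

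**Conclusion.** The concern does not hold. Carried out as written, the plan gives sound answers to its own questions: the Aim 1 means are valid for app users who answer at Week 6, and the 270, the 90, the stopping rule and the models stand unchanged. The effect on any planned estimate is nil. The possible 18 to 72 losses after screening depend on assumed pass rates of 40% to 60% and do not measure install failure, whose frequency and place in the screening sequence the documents leave open. What remains is a preference for fuller reporting, on information the team would probably hold anyway. This conclusion rests on reading the aims as stated. If the rate of successful installation were made an objective, its count and denominator would have to be planned.

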NOTE: Regardless of data and safety monitoring plans by the sponsor or others, the principal investigator is ultimately responsible for protecting the rights, safety, and welfare of subjects under his/her care.

Oversight of internal monitoring of the participants' safety will be conducted by the PI, Dr. [name]. Drs. [name] and [name] will also participate in the development and administration of the plan.

The PI and co-investigators will meet weekly on the project, at which time they will evaluate the progress of the trial, review data quality, recruitment, and study retention, and examine other factors that may affect outcome. They will review the rates of adverse events to determine any changes in participant risk. A brief report will be generated annually for the study record and forwarded to Massachusetts General Hospital's Institutional Review Board. The Investigators will be available to meet outside of the weekly meetings, if necessary, due to concerns regarding a particular participant or any problems that may arise for participants. If necessary, they will make appropriate recommendations for changes in protocol. Dr. [name] will conduct daily oversight of participant safety. She will meet weekly with staff to review participant progress.

Describe the plan to be followed by the Principal Investigator/study staff for review of adverse events experienced by subjects under his/her care, and when applicable, for review of sponsor safety reports and DSMB reports. Describe the plan for reporting adverse events to the sponsor and the Partners' IRB and, when applicable, for submitting sponsor safety reports and DSMB reports to the Partners' IRBs. When the investigator is also the sponsor of the IND/IDE, include the plan for reporting of adverse events to the FDA and, when applicable, to investigators at other sites.

NOTE: In addition to the adverse event reporting requirements of the sponsor, the principal investigator must follow the Partners Human Research Committee guidelines for Adverse Event Reporting

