Any adverse events that are observed and/or reported will be immediately reported to Dr. [name]. Serious adverse events (SAEs) will be reported to the Massachusetts General Hospital IRB immediately by telephone and by written report within 24 hours of our receipt of information regarding the event; SAEs will also be reported in writing to the American Cancer Society. Adverse events will be reported to the Massachusetts General Hospital IRB and the American Cancer Society annually.

MONITORING AND QUALITY ASSURANCE

Describe the plan to be followed by the principal investigator/study staff to monitor and assure the validity and integrity of the data and adherence to the IRB-approved protocol. Specify who will be responsible for monitoring, and the planned frequency of monitoring. For example, specify who will review the accuracy and completeness of case report form entries, source documents, and informed consent.

NOTE: Regardless of monitoring plans by the sponsor or others, the principal investigator is ultimately responsible for ensuring that the study is conducted at his/her investigative site in accordance with the IRB-approved protocol, and applicable regulations and requirements of the IRB.

The PI will oversee the collection, maintenance, and analysis of all data. During weekly meetings with study staff and co-investigators, the PI will review the accuracy and completeness of the study questionnaires, consent forms, and app data. The study procedures and plans will also be reviewed during these meetings to ensure that they remain in line with the approved protocol.

For guidance, refer to the following Partners policies:

Data and Safety Monitoring Plans and Quality Assurance

https://partnershealthcare-

public.sharepoint.com/ClinicalResearch/DSMP in Human Subjects Research.pdf

Reporting Unanticipated Problems (including Adverse Events)

https://partnershealthcare-

public.sharepoint.com/ClinicalResearch/Reporting Unanticipated Problems including Adverse Events.pdf

PRIVACY AND CONFIDENTIALITY

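### Adverse event rates are to guide the safety review, but the plan describes no active way of asking about events in this fully remote study and no denominator for the rate

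*Combined protocol and SAP*

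**What the plan says.** - **Use of the rates.** Data and Safety Monitoring describes weekly meetings of the PI and co-investigators: "They will review the rates of adverse events to determine any changes in participant risk". If necessary, they recommend protocol changes. Adverse events also go to the IRB and the funder once a year.
- **Intake.** The same section gives one rule: "Any adverse events that are observed and/or reported will be immediately reported to" a named investigator. The 24-hour clock for serious events starts when the team receives the information.
- **Setting.** Research Design and Methods: "Our study will be conducted entirely remotely and will require a screening process prior to enrolling participants on the app". The sample size paragraph describes users as "interacting with the app and study staff completely remotely, without the benefit of inperson interaction".
- **Contacts after enrollment.** "Participants will receive survey links for 2-week, 6-week, 3-month and 6-month follow-ups via an emailed link". The one live contact is an optional Skype session after the 6-week survey, for a random 20 of those interested. Its four open questions all concern the app.
- **Survey content that is described.** Ease of use and usefulness of each app feature (Aim 1); "desire to smoke, mood, self-efficacy to quit/stay quit, motivation" (Aim 2); open-ended items meant to find app features needing improvement (Aim 3).
- **Named risks.** Foreseeable Risks and Discomforts lists discomfort from the questionnaires, breach of confidentiality or privacy, and discomfort from quitting, including withdrawal symptoms and craving. All are called minimal.

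**The concern.** A rate needs a numerator collected in the same way from everyone and a stated denominator. The plan gives neither. With no in-person contact there is little for staff to observe, so most events reach the team only if someone reports them, and the protocol does not say that anyone is asked. Desire to smoke and mood are measured, but as outcomes for Aim 2 rather than as safety data. Other withdrawal symptoms and privacy problems have no described question at all.

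Two things are at stake. First, an empty adverse event log could not be read: a group that was asked and had no events would look the same as a group that was never asked. Second, the weekly comparison assumes that events are captured equally well throughout, and the design gives reasons to doubt this. App use is strongly encouraged for 7 weeks and optional afterwards, the only live session comes after week 6, and the gaps between surveys lengthen to three months.

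**Working it through.** **1. The plan's own figures.** The protocol expects 1/3 of those who consent to pass screening and be retained to week 6: 270 × 1/3 = 90, as stated. It gives no adverse event rate, threshold or capture fraction, so there is no safety figure to reproduce.

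**2. Contacts after enrollment.** The remuneration table lists a \$25 phone item at week 6. All items sum to 20 + 25 + 25 + 25 + 50 + 25 + 25 = \$195, the total given with a Skype session. Without that item the sum is \$170, the total given without one. So the week-6 item is the feedback session itself, not a further call made to everyone. That leaves four emailed surveys for all and one session for about 20.

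**3. Denominator.** Any event count gives a rate three times as high over the 90 completers as over the 270 who consent (270/90 = 3). For example, 18 events are 18/90 = 20% or 18/270 = 6.7%. The number who actually start on the app lies somewhere between and is not stated.

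**4. Undercounting (illustration only).** Let p be the true proportion of participants with an event and c the fraction of these recorded. Neither is in the documents, so both are assumed over a range. With n = 90:

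- expected recorded events = 90·p·c
- chance of recording at least one = 1 − (1 − pc)^90
- if none is recorded, the one-sided 95% upper limit on the recorded rate is 1 − 0.05^(1/90) = 3.3%; dividing by c gives the limit on the true rate
- power to see p go from 10% to 20% between two halves of 45 (normal approximation, two-sided 0.05), with c the same in both halves

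| c | Expected events, p = 5% | At least one, p = 5% | At least one, p = 2% | Upper limit on true rate if none recorded | Power, 10% to 20% |
|---|---|---|---|---|---|
| 100% | 4.5 | 99% | 84% | 3.3% | 26% |
| 75% | 3.4 | 97% | 74% | 4.4% | 20% |
| 50% | 2.3 | 90% | 60% | 6.5% | 14% |
| 25% | 1.1 | 68% | 36% | 13.1% | 9% |

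**5. Detecting a change.** The recorded ratio is (p2·c2)/(p1·c1).

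- Constant capture, c = 50%: (0.20 × 0.50)/(0.10 × 0.50) = 2.0. The doubling is preserved, with less precision.
- Capture falling from 50% to 25%: (0.20 × 0.25)/(0.10 × 0.50) = 1.0. The doubling disappears.
- Same fall in capture with no change in risk: (0.10 × 0.25)/(0.10 × 0.50) = 0.5. Risk appears to halve.

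**The case against.** The strongest reply is that silence in the protocol is not absence from the study. A survey answer is also a report, so the intake rule does not exclude solicited events. The lists under Planned Analyses name what will be analyzed, not everything that is asked; the questionnaires are not reproduced, and the open-ended items give respondents a place to mention a problem. This stands. A reader might infer that events enter the record only when volunteered, and the documents do not support that. They support only that no active question is described.

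A reader might also infer that the rates cannot show a change in risk. That does not follow from undercounting alone, because constant capture preserves the ratio (step 5). Small numbers are a limit in any case: even with full capture, power for 10% to 20% is about 26%, and extra survey items will not cure that.

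There are other safeguards: daily oversight of participant safety, extra meetings about individual participants, weekly review of questionnaires for accuracy and completeness, and contact details in the consent form. They matter, but oversight works on the information that arrives, and contact details are a route for volunteering.

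Finally, this is a behavioral pilot with minimal risk whose main aim is qualitative input, and no aim or endpoint depends on adverse event rates. That limits the severity. It does not explain how the rate that the plan itself relies on will be obtained.

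**Conclusion.** The concern holds in a limited form. The plan gives adverse event rates a part in judging participant risk but describes only passive intake and no denominator. Undercounting is likely, and its size is unknown. A change in risk may be missed, or a false one created, if capture varies over time; the design makes such variation plausible but does not prove it. The one figure that comes from the documents alone is the threefold spread between the two possible denominators, 90 and 270. Everything in steps 4 and 5 rests on assumed event rates and capture fractions.

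Two further inferences should not be drawn. The documents do not show that the study would record few or no events whatever happened: at p = 5%, the chance of at least one record is still 68% with c = 25%. Nor do they show that these rates will carry over into the safety plan of Study 3. They say only that Study 3 will be a proof-of-concept RCT of Version 3 of the app.

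This is a modest point, worth acting on because the remedy is cheap.

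**What to change.** Add two or three solicited items to each of the four follow-up surveys (2 weeks, 6 weeks, 3 months, 6 months), with a stated recall window such as the time since the last scheduled survey:

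- any new or worsened health problem or discomfort from quitting, with its severity and whether it led to emergency or hospital care
- any privacy concern linked to the study

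Set a REDCap alert to the PI on any positive answer. If such items already exist, cite them under Data and Safety Monitoring instead.

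In that section, define the reviewed rate at each survey as participants with a solicited event divided by participants who answered the items at that survey. List volunteered events separately. State that non-responders remain unobserved, since survey items cannot reach people who stop engaging, and report the number who answered beside each rate.

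The cost is slightly longer surveys, some minor events to triage, a higher reported event rate and a short IRB amendment. No visits are added, and the surveys are already sent and paid for.
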